6.3.2 Secondary Analysis (or Analysis of Secondary Endpoints)

In addition to the primary analysis, additional analyses will be carried out to determine correlations between sociodemographic and clinical variables, similarity in physician and patient post-consultation reports, quality of life scores, decision-support preferences, decisional conflict, and satisfaction with decision.

All data analyses will be conducted by first using exploratory data techniques to examine univariate and bivariate relationships for statistical significance. Multivariate models will be constructed using statistical criteria, plausibility of associations, the existence of a priori hypotheses, and proposed causal pathways. Chi-square, non-parametric and log-linear techniques will be used for categorical or ordinal data, and t-tests, where appropriate, for continuous data. Multivariate models will use the observed likelihood ratio statistic as a statistical index of model fit. Observed effect sizes and their precision (expressed as 95% confidence intervals) will be more important components of these analyses than the associated p-values.

7 Study Management

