2.2 Secondary

Secondary objectives are to:

1. Determine agreement between patient and physician post-consultation reports of treatments discussed and recommended, prognosis, and expected tolerance.

2. Determine correlations between overall and lung cancer-specific quality of life and decision-support preferences.
3. Determine correlations between overall and lung cancer-specific quality of life and decisional conflict.
4. Determine correlations between overall and lung cancer-specific quality of life and satisfaction with decision.
5. Determine correlations between decision-support preferences and decisional conflict and satisfaction with decision.
6. Determine correlations between decisional conflict and satisfaction with decision.

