5. **Post-Consultation Questionnaire**: The Post-Consultation Questionnaire will be completed by the patient and their oncologist *once after the consultation*. It includes the following components:
 - a. Treatment Recommendations and Decisions: Treatments discussed, recommended, and chosen by the patient and their oncologist will be recorded. Options may include surgery, radiation therapy, chemotherapy, targeted therapy, observation, hospice, no treatment, or unresolved. The oncologist and patient will also be asked for an estimation of the tolerance of the treatment. This information will be obtained from the patient and oncologist *immediately after the consultation*.
 - b. Prognosis Estimates: Estimates of prognosis with no treatment and with the recommended treatment will be obtained from the patient and oncologist *immediately after the consultation*.
 - c. Program Evaluation: The patient will be asked to score the extent to which this process increased their understanding of their cancer treatment options and confidence in their oncologist *immediately after the consultation*.
6. **Satisfaction with Health Care Decision (SWD)**: Although the DCS will provide a general measure of satisfaction with the medical encounter, it does not specifically query the patient's satisfaction with the health care decision itself. The Patient Satisfaction with Health Care Decision (SWD) is a six-item scale with excellent reliability and good discriminant validity. The instrument was validated using a sample of postmenopausal women specifically to evaluate the utility of patient decision aids.¹⁴ The strength of the SWD is that it measures satisfaction with the decision made regardless of how good or bad the prognosis or health outcome might be for the individual patient. The SWD will be completed *once after the consultation*.

7. Acceptability: The PwP website will be monitored for usage *during the consultation and afterwards*. Patients will be given an account to enable continuous, unlimited access for the life of the grant. Usage statistics will be monitored only in aggregate terms, without reference to specific content accessed by individual patients. Repeat visiting to the website will be quantified to establish evidence of acceptance on the part of patients. Physician acceptance will be judged by rates of participation in using the decision aid during the consultation process.

6 Statistical Considerations and Evaluation of Results

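### Secondary objective 1 is patient-physician agreement, but section 6.3.2 names no measure of agreement

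*Combined protocol and SAP*

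**What the plan says.** The first secondary objective in section 2.2, repeated in the synopsis, is: "Determine agreement between patient and physician post-consultation reports of treatments discussed and recommended, prognosis, and expected tolerance". Objectives 2 to 6 in the same list each ask for correlations, so the protocol itself separates agreement from correlation.

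Section 5.1 describes paired data. For treatments: "Treatments discussed, recommended, and chosen by the patient and their oncologist will be recorded". For prognosis: "Estimates of prognosis with no treatment and with the recommended treatment will be obtained from the patient and oncologist". Both parties also estimate how well the treatment will be tolerated.

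Section 6.3.2 carries the objective into the analysis in one clause: "additional analyses will be carried out to determine correlations between sociodemographic and clinical variables, similarity in physician and patient post-consultation reports", followed by quality of life, preferences, decisional conflict and satisfaction. The methods paragraph then covers everything at once. It opens with "All data analyses will be conducted by first using exploratory data techniques to examine univariate and bivariate relationships for statistical significance". The named techniques are "Chi-square, non-parametric and log-linear techniques will be used for categorical or ordinal data, and t-tests, where appropriate, for continuous data", plus multivariate models. It ends with "Observed effect sizes and their precision (expressed as 95% confidence intervals) will be more important components of these analyses than the associated p-values".

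Percent agreement, kappa, weighted kappa, an intraclass or concordance coefficient, and limits of agreement are not mentioned. Similarity is not defined for any questionnaire item.

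**The concern.** Agreement asks whether the two members of a pair gave the same answer. Chi-square and correlation ask whether one answer predicts the other, which is a different question: a patient and an oncologist who regularly give opposite answers are strongly associated. A t-test asks whether the average answers differ, which says little about individual pairs.

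The study collects the agreement data partly to help design later, larger evaluations (sections 1.3 and 6.1.1). An association p-value or a correlation cannot serve as that planning figure. If the analysis follows 6.3.2 as written, its usual outputs would leave objective 1 without an estimate, although the paired data would be in hand.

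**Working it through.** The documents give no target, sample size or expected level for agreement, so there is no figure to reproduce. The check is whether the named methods can give a misleading answer. All tables and parameters below are constructed for illustration. The only input from the documents is 250, the planned enrolment in section 3.1, used as the upper limit on the number of pairs.

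**Formulas for a 2x2 table** with rows (a, b) and (c, d), patient by oncologist, n = a+b+c+d:
- observed agreement po = (a+d)/n
- chance agreement pe = (row 1 x column 1 + row 2 x column 2)/n²
- kappa = (po - pe)/(1 - pe)
- Pearson chi-square = n(ad - bc)²/(product of the four margins)

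**Example 1: 40, 110 / 70, 30.** Rows 150 and 100, columns 110 and 140.
- po = 70/250 = 0.28
- pe = (150x110 + 100x140)/62,500 = 30,500/62,500 = 0.488
- kappa = (0.28 - 0.488)/0.512 = -0.41
- chi-square = 250 x (1,200 - 7,700)²/(150x100x110x140) = 45.7

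The association is strong because the pairs disagree.

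**Example 2: 60, 100 / 10, 80.** Rows 160 and 90, columns 70 and 180.
- po = 140/250 = 0.56
- pe = (160x70 + 90x180)/62,500 = 27,400/62,500 = 0.4384
- kappa = 0.1216/0.5616 = 0.22
- chi-square = 250 x (4,800 - 1,000)²/(160x90x70x180) = 19.9, p < 0.0001

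**Example 3: 230, 10 / 9, 1.** Rows 240 and 10, columns 239 and 11.
- po = 231/250 = 0.924
- pe = (240x239 + 10x11)/62,500 = 57,470/62,500 = 0.9195
- kappa = 0.06
- chi-square = 0.78, p = 0.38

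Here 92% of pairs agree and chi-square is not significant. Kappa is also low because nearly everyone gives the same answer, which is why percent agreement and kappa should be reported together.

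**Numeric reports, systematic shift.** Take equal SDs, correlation 0.8 and patients one SD more optimistic. Lin's concordance coefficient is 2r/(2 + shift²) = 1.6/3 = 0.53, and the correlation stays at 0.8. A paired t-test does see the shift: the SD of the difference is sqrt(2(1 - 0.8)) = 0.632 SD, so t = sqrt(250)/0.632 = 25.

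**Numeric reports, no shift.** In a simulated sample of 250 unrelated pairs with SD 15 and means set equal, the t-test gives p = 1.0, the concordance coefficient is -0.05 and the limits of agreement are about ±43 points. The theoretical value is 1.96 x 15 x sqrt(2) = 41.6. The t-test is null and the pairs disagree widely.

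**Precision of the remedy.** Assume chance agreement 0.50 and 250 pairs, with SE(kappa) = sqrt(po(1 - po)/(n(1 - pe)²)):

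| Assumed agreement | kappa | 95% CI |
|---|---|---|
| 0.60 | 0.20 | 0.08 to 0.32 |
| 0.70 | 0.40 | 0.29 to 0.51 |
| 0.80 | 0.60 | 0.50 to 0.70 |

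The half-width is 0.10 to 0.12. Fewer complete pairs would widen it.

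**The case against.** A reader might infer that the plan has chosen chi-square, correlation and t-tests for agreement. It has not. The methods sentence is a general list sorted by data type, and no sentence ties any of those tests to objective 1. The list also includes non-parametric and log-linear techniques, and log-linear models can be set up for agreement. This objection stands: the documents support the statement that no agreement measure is named, and not that a wrong one was assigned. But the paragraph claims to cover all data analyses and nothing else covers objective 1, so the gap is real. A non-parametric paired test would assess a shift, not agreement within pairs.

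A reader might also infer that every listed test misleads by being significant under disagreement, or that patient optimism about prognosis would go unseen. Neither holds for the t-test. A significant paired t-test correctly signals systematic disagreement. Its weakness is the null result that hides disagreement within pairs. The plan does not say that the test would be paired.

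A third argument is that "similarity in physician and patient post-consultation reports" may be meant as a score derived for each pair and then related to other variables, for which the listed tests are ordinary tools. That is a fair reading of 6.3.2. It still leaves similarity undefined, and relating such a score to other variables does not estimate the level of agreement that section 2.2 asks for.

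Last, the plan ranks effect sizes and intervals above p-values. This makes it unfair to predict that a bare significance test would be reported as agreement. It does not say which effect size would be reported, and the usual ones for chi-square or correlation measure association.

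**Conclusion.** The point holds as an under-specification. Objective 1 is agreement, and 6.3.2 neither names a measure of it nor defines similarity. The listed methods in their usual form yield association or mean-difference results, which can part company with agreement in either direction: a chi-square of 45.7 with 28% agreement, or 0.78 with 92% agreement.

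These examples show what can happen, not what is expected in this trial, because the documents give no agreement levels. The response scales for prognosis and tolerance are not in the text available here, so the right measure for those items depends on whether they are ordered categories or numbers. The consequence is confined to one secondary objective meant to provide preliminary data. The primary analysis and the sample size are untouched. The sponsor should make the change, but the study does not depend on it.

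**What to change.** Add one sentence to section 6.3.2 stating that objective 1 will be analysed as follows:

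- for each treatment option discussed or recommended: percent agreement and kappa, each with a 95% CI;
- for ordinal tolerance or prognosis categories: weighted kappa with a 95% CI, with the weights stated;
- for any numeric prognosis estimate: the mean paired difference with limits of agreement.

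Keep the chi-square, non-parametric, log-linear and t-test methods for the association objectives. If a similarity score for each pair is also to be related to other variables, define it there. Several patients will probably share an oncologist, so it would be sensible for the intervals to allow for that clustering.

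The cost is this short text change. The data already planned in section 5.1 suffice, and no extra patients or questionnaires are needed.

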7.1 Pre-study Documentation

This study will be conducted in accordance with the ethical principles that have their origin in the Declaration of Helsinki as stated in 21 CFR §312.120(c)(4); consistent with GCP and all applicable regulatory requirements.

Before initiating this trial, the Investigator will have written and dated approval from the Institutional Review Board for the protocol, written informed consent form, subject recruitment materials, and any other written information to be provided to subjects before any protocol related procedures are performed on any subjects.

The Investigator must comply with the applicable regulations in Title 21 of the Code of Federal Regulations (21 CFR §50, §54, and §312), GCP/ICH guidelines, and all applicable regulatory requirements. The IRB must comply with the regulations in 21 CFR §56 and applicable regulatory requirements.

7.2 Institutional Review Board Approval

The protocol, the proposed informed consent form, and all forms of participant information related to the study (e.g. advertisements used to recruit participants) will be reviewed and approved by the UCSF CHR (UCSF Institutional Review Board). Prior to obtaining CHR approval, the protocol must be approved by the Helen Diller Family Comprehensive Cancer Center Site Committee and by the Protocol Review Committee (PRC). The initial protocol and all protocol amendments must be approved by the IRB prior to implementation.

7.3 Informed Consent

All participants must be provided a consent form describing the study with sufficient information for each participant to make an informed decision regarding their participation. Participants must sign the CHR-approved informed consent form prior to participation in any study specific procedure. The participant must receive a copy of the signed and dated consent document. The original signed copy of the consent document must be retained in the medical record or research file.

7.4 Changes in the Protocol

Once the protocol has been approved by the UCSF CHR, any changes to the protocol must be documented in the form of an amendment. The amendment must be signed by the Investigator and approved by PRC and the CHR prior to implementation.

If it becomes necessary to alter the protocol to eliminate an immediate hazard to patients, an amendment may be implemented prior to CHR approval. In this circumstance, however, the Investigator must then notify the CHR in writing within five (5) working days after implementation. The Study Chair and the UCSF study team will be responsible for updating any participating sites.

7.5 Data Storage and Confidentiality

Patient confidentiality will be ensured at all times. Study results will not be released to participants. Patient identifiers will not be accessible to associated research scientists or clinicians conducting the research unless subsequently approved through the CHR. De-identified clinical and laboratory information may be shared with other investigators at other institutions. There are currently no plans to contact patients to inform them about

any finding of the study. Patient identifiers will not be made available to any other hospitals, insurers, or agencies. The results of studies emerging from this work may be published but individual patients will not be identifiable in these publications.

7.6 Record Keeping and Record Retention

The Principal Investigator is required to maintain adequate records.

The Principal Investigator is required to prepare and maintain adequate and accurate case histories that record all observations and other data pertinent to the investigation on each individual administered the intervention in the investigation. Case histories include the case report forms and supporting data (e.g., signed and dated consent forms and medical records, such as progress notes of the physician, the individual's hospital chart(s), and the nurses' notes. The case history for each individual shall document that informed consent was obtained prior to participation in the study.

Study documentation includes all CRFs, data correction forms or queries, source documents, Sponsor-Investigator correspondence, monitoring logs/letters, and regulatory documents (e.g., protocol and amendments, CHR correspondence and approval, signed patient consent forms).

Source documents include all recordings of observations or notations of clinical activities and all reports and records necessary for the evaluation and reconstruction of the clinical research study.

In accordance with FDA regulations, the investigator shall retain records for a period of 2 years following the date a marketing application is approved for the drug for the indication for which it is being investigated; or, if no application is to be filed or if the application is not approved for such indication, until 2 years after the investigation is discontinued and FDA is notified.

8 Protection of Human Subjects

8.1 Protection from Unnecessary Harm

Each clinical site is responsible for protecting all subjects involved in human experimentation. This is accomplished through the CHR mechanism and the process of informed consent. The CHR reviews all proposed studies involving human experimentation and ensures that the subject's rights and welfare are protected and that the potential benefits and/or the importance of the knowledge to be gained outweigh the risks to the individual. The CHR also reviews the informed consent document associated with each study in order to ensure that the consent document accurately and clearly communicates the nature of the research to be done and its associated risks and benefits.

Appendix 1a Questionnaires - Patient

Decision Making Preference Questionnaire

After they have all the information they need about their illness and possible treatments, some patients prefer to leave decisions about their treatment up to their doctor, while others prefer to participate in these decisions. Please check the statement that best describes what you believe would be ideal.

- The **doctor** should make the decisions using all that's known about the treatments.
- The **doctor** should make the decisions but strongly consider my opinion.
- The **doctor and I** should make the decisions together on an equal basis.
- I** should make the decisions, but strongly consider the doctor's opinion.
- I** should make the decisions using all I know or learn about the treatments.

FACT-L (Version 4)

Below is a list of statements that other people with your illness have said are important. **Please circle or mark one number per line to indicate your response as it applies to the past 7 days.**

PHYSICAL WELL-BEING		Not at all	A little bit	Some-what	Quite a bit	Very much
GP1	I have a lack of energy	0	1	2	3	4
GP2	I have nausea	0	1	2	3	4
GP3	Because of my physical condition, I have trouble meeting the needs of my family	0	1	2	3	4
GP4	I have pain	0	1	2	3	4
GP5	I am bothered by side effects of treatment	0	1	2	3	4
GP6	I feel ill	0	1	2	3	4
GP7	I am forced to spend time in bed	0	1	2	3	4
SOCIAL/FAMILY WELL-BEING		Not at all	A little bit	Some-what	Quite a bit	Very much
GS1	I feel close to my friends	0	1	2	3	4
GS2	I get emotional support from my family	0	1	2	3	4
GS3	I get support from my friends	0	1	2	3	4
GS4	My family has accepted my illness	0	1	2	3	4
GS5	I am satisfied with family communication about my illness	0	1	2	3	4
GS6	I feel close to my partner (or the person who is my main support)	0	1	2	3	4
Q1	Regardless of your current level of sexual activity, please answer the following question. If you prefer not to answer it, please mark this box  and go to the next section.					
GS7	I am satisfied with my sex life	0	1	2	3	4

FACT-L (Version 4)

Please circle or mark one number per line to indicate your response as it applies to the past 7 days.

EMOTIONAL WELL-BEING

	Not at all	A little bit	Some- what	Quite a bit	Very much
--	---------------	-----------------	---------------	----------------	--------------

GE1	I feel sad	0	1	2	3	4
GE2	I am satisfied with how I am coping with my illness.....	0	1	2	3	4
GE3	I am losing hope in the fight against my illness.....	0	1	2	3	4
GE4	I feel nervous.....	0	1	2	3	4
GE5	I worry about dying.....	0	1	2	3	4
GE6	I worry that my condition will get worse.....	0	1	2	3	4

FUNCTIONAL WELL-BEING

	Not at all	A little bit	Some- what	Quite a bit	Very much
--	---------------	-----------------	---------------	----------------	--------------

GF1	I am able to work (include work at home)	0	1	2	3	4
GF2	My work (include work at home) is fulfilling.....	0	1	2	3	4
GF3	I am able to enjoy life.....	0	1	2	3	4
GF4	I have accepted my illness.....	0	1	2	3	4
GF5	I am sleeping well	0	1	2	3	4
GF6	I am enjoying the things I usually do for fun	0	1	2	3	4
GF7	I am content with the quality of my life right now.....	0	1	2	3	4

FACT-L (Version 4)

Please circle or mark one number per line to indicate your response as it applies to the past 7 days.

ADDITIONAL CONCERNS		Not at all	A little bit	Some-what	Quite a bit	Very much
B1	I have been short of breath	0	1	2	3	4
C2	I am losing weight.....	0	1	2	3	4
L1	My thinking is clear	0	1	2	3	4
L2	I have been coughing	0	1	2	3	4
B5	I am bothered by hair loss	0	1	2	3	4
C6	I have a good appetite	0	1	2	3	4
L3	I feel tightness in my chest.....	0	1	2	3	4
L4	Breathing is easy for me	0	1	2	3	4
Q3	Have you ever smoked? No ____ Yes ____ If yes:					
L5	I regret my smoking	0	1	2	3	4

Decisional Conflict Scale (DCS)

	Strongly Agree	Agree	Neither Agree Nor Disagree	Disagree	Strongly Disagree
I know which options are available to me.					
I know the benefits of each option.					
I know the risks and side effects of each option.					
I am clear about which benefits matter most to me.					
I am clear about which risks and side effects matter most to me.					
I am clear about which is more important to me (the benefits or the risks and side effects).					
I have enough support from others to make a choice.					
I am choosing without pressure from others.					
I have enough advice to make a choice.					
I am clear about the best choice for me.					
I feel sure about what to choose.					
This decision is easy for me to make.					
I feel I have made an informed choice.					
My decision shows what is important to me.					
I expect to stick with my decision.					
I am satisfied with my decision.					

AM O'Connor, Decisional Conflict Scale. ©1993 [updated 2005]. Available from www.ohri.ca/decionaid.
